7.2.2 OTHER ASSAYS OR PROCEDURES

Not applicable.

7.2.3 SPECIMEN PREPARATION, HANDLING, AND STORAGE

Phosphatidyl ethanol (PEth) Testing by Dried Blood Spot Collection

Phosphatidyl ethanol (PEth) are a series of abnormal phospholipids located in the cell membrane and formed in the presence of ethanol and phospholipase D. PEth serves as a biomarker of alcohol ingestion in the past 2-3 weeks using liquid chromatography tandem mass spectrometric assessment of human blood (whole or dried spots). PEth is not significantly affected by age, gender, or medical disease.

Dried blood spots offer numerous advantages over venipuncture including reduced costs, invasiveness and discomfort. Five dried blood spots are obtained from a finger puncture onto a lab provided collection card. The collection is performed by the participant under the observation of the study team staff. Sample results are available to the study team via the commercial lab's portal using a study specific username/password combination and the unique non-PHI identifier on the blood spot collection card. NOTE: For this study, only the unique study participant number is used to identify the sample. The chain of custody process as

described in the instruction sheet and video (participant signature, picture identification card, participant name, etc.) is not applicable to this protocol.

Serum Buprenorphine

Buprenorphine and its metabolite norbuprenorphine are assayed using liquid chromatography tandem mass spectrometry by a commercial laboratory. Approximately 2.5 to 10 mL of blood will be collected by a trained phlebotomist into a red-top tube. The sample is allowed to clot and then centrifuged to separate the serum from the cells before transferring the serum into a standard transport tube labeled with a unique study participant code. Sample results are available via the commercial laboratory portal using a study specific username/password combination and the unique participant code/requisition number.

7.2.4 SPECIMEN SHIPMENT

The PEth collection card is placed in the box provided and shipped in a standard cardboard (non-plastic) envelope along with the laboratory requisition form to the commercial lab using tracked carrier such as FedEx or UPS. Biohazard shipping labels are not required for this type of specimen. The dried blood specimens are stable, without refrigeration, thus they do not require overnight shipping, ice packs, or dry ice for shipping.

Buprenorphine sample(s) and lab requisition form are transported to the commercial lab using tracked carrier such as FedEx/UPS or by direct pick-up by a commercial lab courier (available at some sites). Samples should be shipped overnight, at ambient temperature (no dry ice required) using IATA guidelines in a UN 3373 Overpack (Biological Substance Category B) envelope.

So that local sites remained masked from serum BUP levels, lab results will be securely provided to the DCC. Samples and subsequent results will be identified only by the unique participant ID and the visit week.

7.3 STUDY SCHEDULE

7.3.1 SCHEDULE OF ASSESSMENTS

Assessments	Schedule of Assessments: Screening, Baseline, Week (#) or Telephone (T) Visit																	
	Screen	Baseline	Baseline (Day 2)	Week 1	Week 2	T	Week 4	T	Week 6	T	Week 8	Week 8 (Day 2)	T	Week 10	T	Week 12	T	Week 14
Assessments to Qualify for Study and Characterize Population																		
Demographics	X																	
Smoking Status*	X										X					X		
MINI-5	X																	
H&P**	X																	
VS, BMI, BrAC	X	X		X&	X&		X		X&		X			X&		X		X
Labs/ECG**	X							X**			X**					X		
Pregnancy	X						X				X					X		
CIWA-Ar	X	X														X		X
COWS	X															X		X
ADS	X																	
OSU-TBI	X																	
BIS	X																	
Psychophysiology Study																		
Fear Conditioning			X ⁺								X ⁺							
Psychophys. Tests				X ⁺		X ⁺					X ⁺	X ⁺						
Alcohol Related Outcomes																		
TLFB	X	X		X	X		X		X		X			X		X		
OCDS		X		X	X		X		X		X			X		X		
Peth	X										X					X		
Serum BUP											X					X		
SIP	X										X					X		
DAQ	X				X						X							
Urine Drug Screen	X	X				X					X					X		
PTSD Related Outcomes																		
LEC-5 Checklist	X																	
PCL-5	X	X		X	X		X		X		X			X		X		
CAPS-5***		X				X					X					X		
Psychological Symptoms and Quality of Life																		
C-SSRS****	X	X										X						
PHQ-9		X					X					X					X	
VR-12	X										X					X		
CGI-S	X						X				X					X		
CGI-I							X				X					X		
Adverse Events and Concomitant Medications																		
Con-Meds	X	X		X	X		X		X		X			X		X		X
Adverse Events				X	X	X	X	X	X	X	X	X		X	X	X	X	X
Study Drug***																		
Dispense Drug		X					X					X\$						
Pill Counts				X	X		X		X		X			X		X		
Study Drug Knowledge																X		

*Smoking: Will include both tobacco and marijuana at baseline, and marijuana only at Weeks 8 and 12. **H&P, laboratory tests, and ECG within previous 90 days is acceptable at screening visit. (At Week 12: The H&P, thyroid test, and ECG do not need to be repeated.) If baseline level was between 3x-5x ULN, ALT and AST needs to be repeated at week 4 and week 8 visit. At Week 8, GGT needs to be repeated. ^aVital signs and breathalyzer on Week 2, 6, 10 may be omitted due to COVID-19 reduction of in-person visits. ^bPsychophysiological assessments are optional so as to not be a barrier to enrollment or randomization. ***Day of Randomization is on Baseline. The schedule of follow-up visits is anchored to Baseline. ****CAPS-5 and C-SSRS can be administered prior to day of baseline so long as it is within one week of day of randomization and scores are entered as baseline. ****C-SSRS can be done either at screening or baseline visit, as well as Week 8. ^{\$}Baseline and week 8 drug dispensing will occur on day 1 if not participating in psychophysiology testing and on day 2 if participating in testing

7.3.2 SCREENING

During the process of informed consent and screening, the investigators and CRCs provide thorough pre-enrollment education for all prospective participants and confirm the participant's commitment to and feasibility for follow-up. Screening and baseline visits are separate from day of randomization so that any ambivalence can manifest, and participants can back-out prior to randomization.

Screening takes place over 1 to 14 days and includes the study instruments listed in table above and laboratory tests described in section 7.2. A history and physical (H&P) and ECG within the prior 90-days is acceptable for the study screening purposes; otherwise, it should be repeated. Laboratory tests (except for pregnancy tests and urine drug screens) performed within 90 days of screening are acceptable for study screening purposes. All laboratory test results are reviewed by the investigator or qualified designee and acknowledged. Any value outside of the normal range is flagged and the investigator determines whether it is clinically significant. If a test is questionable, the test(s) may be repeated, or additional testing done to provide clarification. Unscheduled laboratory testing may be done at the discretion of the investigator for appropriate medical care.

At any point in the screening process and based on the inclusion and exclusion criteria listed above, the participant may be deemed eligible and proceed to baseline visit or investigator may exclude a participant and refer him/her for appropriate treatment.

Participants **should not** be taken off psychotropic or disallowed medications for purposes of entering the study. However, he/she can work with their provider to discontinue and washout excluded medication(s) that are not clinically indicated or effective and subsequently be referred to the study. A participant who is otherwise meeting eligibility criteria except for taking an excluded medication can undergo a medically supervised discontinuation and 5-day (or longer if indicated) washout of medication(s), if representative of the clinical plan regardless of study participation, (i.e., psychotropic medications are only be discontinued for washout if the consenting participant is not tolerating or not responding to the medication).

At screening and baseline, the investigators will evaluate the participant for signs and symptoms of acute withdrawal from alcohol. In addition to vital signs and participant verbal history, the Clinical Institute Withdrawal Assessment (CIWA-Ar) will be used to facilitate assessment of withdrawal, and decisions regarding appropriateness for study entry and continuation with respect to physical dependence will be made by the investigators based on the judgment of study physicians. We will use a CIWA-Ar score of ≤ 8 for an approximate cutoff level for inclusion into the study. A CIWA-Ar score of 10 – 15 indicates a need for medical treatment, which may include chlordiazepoxide (Librium), benzodiazepines, or anticonvulsants (in addition to thiamine and folate). All our study physicians have extensive experience in assessing and triaging patients who may be experiencing alcohol withdrawal. Participants that show signs or symptoms of alcohol withdrawal and who need detoxification will be referred for detoxification at the local outpatient clinic or an inpatient unit (depending on the level of care needed) and

managed according to local VA Center Memorandum or policies for managing alcohol withdrawal.

If it is in the best interest of the patient, the investigators may begin standard treatment for alcohol withdrawal without delay for a referral or outpatient MD or APN in mental health or primary care (i.e., not research activity). After detoxification, the participant may be eligible for the study at a later time under re-consent and re-screening. In addition, at any time during the course of the study, if relapse into heavy drinking has occurred, the investigators may repeat the CIWA-Ar as needed to evaluate need for exit from the study and medical detoxification. The CIWA-Ar is repeated at the conclusion of the 12-week medication treatment period and at the week-14 follow-up visit to confirm that the patient is medically stable and can be referred to usual care treatment without the need for treatment for withdrawal.

7.3.3 BASELINE AND RANDOMIZATION VISITS

The investigators and CRCs provide ongoing support and education during the study to reinforce the participants' commitment and resolve logistical barriers to keeping the appointments. Participant burden is kept to a minimum (i.e., small number of assessments and low frequency). Adherence and attendance are vital to the success of both treatment and the study. Patient education on study procedures and the treatment approach in the study is the cornerstone to promote adherence. To maximize participant retention, study coordinators are trained to have a substantial focus, especially in the first several meetings with participants, on developing a strong alliance, educating them about the study, understanding the importance of adhering to treatment, what is expected of them as a study participant, and eliciting commitment.

At the baseline visit, the research team evaluates the participant per the study instruments listed in the Schedule of Assessments table in 7.3.1. Participants undergoing the optional two-day psychophysiological assessments, as described above, will complete both days of the psychophysiological testing prior to beginning the study medication.

The research medication provider enters the medication orders (one for XR-NTX and one for SL-BUP) and the local site pharmacy dispenses the study medication according to the randomized assignment to one of two treatments:

- **Treatment A (SL-BUP 2mg + XR-NTX 380mg) or**
- **Treatment B (SL-PLC and XR-PLC).**

SL-BUP is taken daily and XR-NTX is given every 4 weeks. All medications are dispensed by local site pharmacies with clearly labeled instructions.

The participant receives the first dose of XR-NTX injectable in the research clinic and remains in the clinic under the supervision of the research team for approximately 1 hour after the 1st dose is administered.

The medication provider or trained CRC reviews the medication instructions with the participant (how to administer sublingual, keeping up with medication dosing, and need to return any

unused medication to the research medication provider at the next visit). The participant initiates SL-BUP on the following day.

7.3.4 FOLLOW-UP VISITS

Assessments occur at screening, baseline, and post-randomization Weeks 1, 2, 4, 6, 8, 10, and 12. There is a visit window of +/- 7 days for follow-up visits.

The investigators and CRCs provide ongoing reinforcement of the patients' commitment to long-term follow-up. The study medication providers emphasize the need to properly adhere to prescribed treatments or to call to revise the treatments if side effects occur or therapeutic effects are lost.

Adherence to SL-BUP medication is confirmed by pill count. Concomitant medications are updated at each of these visits.

If participants experience side effects that cannot be managed by adjustments in the timing of the medication (i.e., taking at bedtime, etc.), they may have their medication titration either held or the medication dosing may be decreased (i.e., less frequent).

The CRC makes a telephone (t) contact with the participant between face-to-face visits to remind the participant of the next office visit and to check on adherence to the study medication and if there have been any serious adverse events.

*Psychophysiological assessments are optional to not be a barrier to enrollment or randomization.

The one-day psychophysiological assessment is repeated at Week 2.

The two-day psychophysiological assessment is repeated at Week 8.

At Week 8, the participant remains on the assigned treatment and dose from Week 8 to Week 12.

While every attempt is made to retain the participant in the study on medication for the full 12 weeks, the participant may discontinue medication at any point and remain in the study for assessments through Week 12.

7.3.5 FINAL STUDY VISITS

At Week 12, the study medication is discontinued, and all Week 12 assessments are completed. At Week 12, the participant is referred back to his/her previous or newly assigned long-term PTSD provider for follow-up and continued treatment. At Week 14, the participant is assessed for discontinuation or withdrawal side effects and resolution or emergence of adverse events. The participant's ongoing clinical treatment plan is confirmed.

7.3.6 EARLY TERMINATION VISIT

If a participant exits prior to Week 8, all procedures for Week 8 are completed. If the participant exits after Week 8 but prior to Week 12, all Week-12 procedures are completed.

7.3.7 COVID-19 SAFETY PRECAUTIONS

COVID-19 Safety Precautions:

1. Adhere to local VA or University policies or mandates, for example:
 - a. Screening before entering the facility, which may include a 'no touch' method to check temperature and COVID-19 screening questions.
 - b. Participants encouraged or required to wear facial covering/mask while in the buildings, as mandated by the facility.
 - c. Anyone who screens positive for COVID-19 (exposure or symptoms) and/or has a fever will be rescheduled (and possibly tested for COVID-19 as deemed clinically appropriate).
2. Study staff:
 - a. The research team will monitor scheduling of participants in order to allow for social distancing and cleaning procedures between participant visits.
 - b. Research staff members will sanitize high-touch surfaces before and after each in-person visit with disinfectant wipes or sprays.
 - c. Staff members will adhere to local policies regarding wearing protective facial masks, frequent handwashing/use of alcohol-based hand sanitizer, and social distancing.
 - d. Visits will take place in a large enough space so that study staff and the participant can practice social distancing.
 - e. As much as possible, self-assessment forms should be completed via telehealth or phone; and can be given directly to or mailed to the participant in advance of any appointment.
 - f. If the patient desires to complete in-person visit forms on site, staff will honor that request, but maintain social distancing.
 - g. Participants will receive compensation for visits. As needed, study staff will verify their current address in order to be able to mail compensation to the participant.
3. In-Person visits:
 - a. The in-person research visits will be restricted to those that are clinically essential (screening, baseline, Week 4, Week 8, Week 12, and Week 14; due to required labs and/or medication injections).
4. Telehealth/Phone visits:
 - a. Week 1, 2, 6, & 10 visits may be conducted over the phone or telehealth to limit the participants contact (study staff and time in the clinic).
5. Week 14 Visit:
 - a. Week 14 is highly preferred to be conducted in-person or by telehealth due to need for safety check and treatment planning (not as easy to assess over phone without video component).
 - b. At this visit, participant has been off study medications for 2 weeks. Investigators would like to visually assess participants for withdrawal symptoms.
 - c. All safety precautions will be followed during these visits to protect participant and study staff members.

7.4 JUSTIFICATION FOR SENSITIVE PROCEDURES

Not applicable.

7.5 PROHIBITED MEDICATIONS, TREATMENTS, AND PROCEDURES

Due to the potential drug: drug interactions (e.g., opiates) or confounding therapeutic effects (e.g., naltrexone or acamprosate), participants may not use the medications listed in the table below, unless authorized by PASA medical monitor and approved by the lead PIs.

PROHIBITED MEDICATIONS		
Opioids		
Abstral, Actiq, Duragesic, Fentora, Onsolis (fentanyl)	Exalgo (hydromorphone hydrochloride)	Oxycet, Percocet, Roxicet, Xartemis XR (oxycodone/acetaminophen)
Anexsia, Co-Gesic, Hycet, Lorcet, Lortab, Liquicet, Maxidone, Norco, Vicodin, Xodol, Zolvit, Zydome (hydrocodone/ acetaminophen)	Hycodan, Hydromet (hydrocodone/ homatropine)	Percodan (oxycodone/ aspirin)
Avinza, Kadian (morphine sulfate)	Hysingla (hyrocodone)	Rezira (hydrocodone/ pseudoephedrine)
Butrans (buprenorphine)	Ibudone, Reprexain, Vicoprofen	Targiniq ER (oxycodone/ naloxone)
Demerol (meperidine)	Morphabond, Oramorph, Roxanol-T, Sublimaze (morphine)	TussiCaps and Tussionex, Vituz (hydrocodone/ chlorpheniramine)
Dilauidid, Zohydro ER (hydromorphone)	Nucynta ER (tapentadol)	Tylenol #3 and #4 (codeine/ acetaminophen)
Dolophine, Methadose (methadone)	Oxaydo, Xtampza ER (oxycodone)	Zutripro (hydrocodone/ chlorpheniramine/ pseudoephedrine)
Embeda (morphine/ naltrexone)	OxyContin, Palladone (oxycodone hydrochloride)	
Medications Used to Treat AUD		
Antabuse (disulfiram)	Revia (naltrexone hydrochloride)	
Campral (acamprosate)	Vivitrol (extended-release naltrexone as a non-study drug)	
Medications Thought to Effect ETOH Consumption		
Gablofen, Lioresal (baclofen, muscle relaxant)	Topamax (topiramate; also listed under mood stabilizer)	
Zofran (ondansatrin; prevents nausea and vomiting)		
Stimulants and/or ADHD Treatment		
Adderall (amphetamine, dextroamphetamine)	Dexedrine (dextroamphetamine)	Vyvanse (lisdexamfetamine)

PROHIBITED MEDICATIONS		
Desoxyn (methamphetamine)	Ritalin, Concerta (methylphenidate)	
Antipsychotics (except for quetiapine that may be used for insomnia)		
Benperidol (benperidol)	Mellaril (thioridazine)	Saphris or Sycrest (asenapine)
Clozaril, FazaClo, Versacloz (clozapine)	Moban (molindone)	Serentil (mesoridazine)
Geodon (ziprasidone)	Navane (thiothixene)	Stelazine (trifluoperazine)
Haldol (haloperidol)	Orap (pimozide)	Trilafon (perphenazine)
Invega (paliperidone)	Prolixin (fluphenazine)	Vraylar (cariprazine)
Latuda (lurasidone)	Risperdal (risperidone)	Zyprexa, Zydis (olanzapine)
Loxitane (loxapine)	Ruxulti (brexpiprazole)	
Alzheimer's Medications		
Aricept (donepezil)	Reminyl (galantamine)	
Benzodiazepine/ Other Sedatives		
Ativan (lorazepam)	Luminal (phenobarbital)	Thorazine (chlorpromazine)
Belsomra (suvorexant)	Novo-Clopate, Traxene (clorazepate)	Traxene (clorazepate)
Diastat, Valium (diazepam)	Prosom, Eurodin (estazolam)	Valium (diazepam)
Frisium, Onfi, Tapclob, Urbanol (clobazam)	Restoril (temazepam)	Vistaril (hydroxyzine)
Gabitril (tiagabine)	Rozerem (ramelteon)	Xanax (alprazolam)
Klonopin (clonazepam)	Novo-Clopate, Traxene (clorazepate)	
Librium (chlordiazepoxide)	Serax (oxazepam)	
Mood Stabilizers (except for lamotrigine that may be used in this population)		
Depakote, Depakene (valproic acid/sodium valproate, divalproex)	Kepra (levetiracetam)	Tegretol (carbamazepine)
Eskalith, Lithobid (lithium)	Trileptal (oxcarbazepine)	Topamax (topiramate)

Due to the potential confounding therapeutic effects of psychotherapy,⁴³ concurrent evidence-based psychotherapy for PTSD (EMDR, Cognitive Processing Therapy, Prolonged Exposure, and cognitive behavioral therapy) are not allowed during the study. Participants who want this type of treatment may enroll in a course of treatment and complete it prior to the study participation.

If a participant develops suicidal, homicidal, or psychotic symptoms or a significant exacerbation of depression or anxiety, that clinically requires non-protocol allowed psychotropic medications,

the individual is withdrawn from the study and treated by a mental health provider in the appropriate setting.

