5.4 PARTICIPANT WITHDRAWAL OR TERMINATION

5.4.1 REASONS FOR WITHDRAWAL OR TERMINATION

Participants may discontinue study treatment or withdraw from participation in the study at any time without cause or reason. Participants may stop study medication but are encouraged to

remain in the study for follow-up assessments. The investigator may discontinue study treatment for a participant or withdraw a participant from the study for one or more of the following reasons:

- The participant's expressed desire to end his/her participation in the study.
 - Note: The participant may choose to stop the study drug but continue in the study for data collection and is thus not withdrawn from the study.
- A clinically significant adverse event (AE), laboratory abnormality, or other medical condition or situation that makes continued participation in the study to be not in the best interest of the participant
- The participant demonstrates an inability to comply with the verbal and written study instructions and/or procedures, (i.e., loses the capacity to provide informed consent)
- The participant exhibits unsafe behaviors (e.g., abusive, aggressive) or becomes suicidal, homicidal, or psychotic, (i.e., at significant risk of harming self or others).
- The participant has an intolerable adverse reaction to a study medication.
- The participant's underlying condition is worsening and needs alternative treatment(s)
- The study is canceled by the PASA Consortium, DoD, or investigators.
- The study is closed by the Data Safety and Monitoring Board (DSMB), Institutional Review Board (IRB), or other oversight committee.
- New information regarding the safety of a study medication emerges that changes the risk benefit profile for a sub-group of participants

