5.4.2 HANDLING OF PARTICIPANT WITHDRAWALS OR TERMINATION

If an early exit occurs, the reason(s) for early termination is documented and all Week 12 procedures are conducted. A post-study phone call or visit is scheduled with the research team to ensure that the participant has made or scheduled the appropriate follow-up appointments and to address any clinical problems or AEs that may have occurred.

Participants may stop study medication but are encouraged to remain in the study for follow-up assessments. In this case, the participant may attend assessments for data collection or consent to allow for continued follow-up through chart review. If a participant withdraws from the interventional portion of a study and does not consent to continued follow-up of associated clinical outcome information, then the investigators will not access the participant's medical record or make future contact with the participant. If a study participant withdraws consent for study participation, then the participant is excluded from all future study procedures and treatments. No additional study data is collected from the participant after consent has been withdrawn.

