		
The TLFB assessment is given at screening, baseline, and weeks 1, 2, 4, 6, 8, 10, and 12. The screening measurement uses a 90-day recall period whereas the subsequent (post treatment follow up) measurements use a recall period of “since the last measurement.” The baseline WHO risk level will be derived from TLFB data collected at both the screening and baseline visit. The look-back period to define the WHO risk level will be conducted over 28 consecutive days and based on the average number of reported standard drinks during those 28 consecutive days. Each derived outcome measure for a specific timepoint will be based on the baseline visit date. In the event 28 consecutive days are not captured for the full look-back period, participant data will be excluded from analyses in the event the number of total days included in look-back period is less than one standard deviation of the entire population.

Percent Heavy Drinking Days (%HDD)	Continuous (range between 0 and 100)	
Percent Heavy Drinking Days (%HDD) is measured via the Timeline Follow Back instrument (Sobell et al., 1996). The screening (baseline) measurement uses a 90-day recall period whereas the subsequent (post treatment follow up) measurements use a recall period of “since the last measurement.” Baseline %HDD will be derived from TLFB data collected at both the screening and baseline visit. The look-back period to define %HDD will be conducted over 28 consecutive days and based on the number of heavy drinking days reported during this time period. Each derived outcome measure for a specific timepoint will be based on the baseline visit date. In the event 28 consecutive days are not captured for the full look-back period, participant data will be excluded from analyses in the event the number of total days included in look-back period is less than one standard deviation of the entire population.
 
A heavy drinking day is defined as follows:
 
>4 standard drinks/sessions for men and >3 standard drinks/sessions for women

Variable	Type	Definition
CAPS-5 Total Symptom Severity Score	Continuous (range between 0 and 80)	CAPS-5 total symptom severity score is measured via the Clinician-Administered PTSD Scale For DSM-5 (CAPS-5). The score is calculated by summing severity scores for the 20 DSM-5 PTSD symptoms (Weathers et al., 2013), with a higher score indicating worse PTSD symptoms.
Exploratory Outcomes		

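### Protocol 7.5 makes study withdrawal mandatory when deterioration needs a non-allowed psychotropic, where 5.4.1 leaves a choice; some outcomes at the scheduled Week 8 time may be lost

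*Protocol*

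**What the plan says.** Protocol 7.5 sets a mandatory rule. If the listed symptoms clinically require a psychotropic that the protocol does not allow, "the individual is withdrawn from the study and treated by a mental health provider in the appropriate setting".

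Protocol 5.4.1 is discretionary: "The investigator may discontinue study treatment for a participant or withdraw a participant from the study for one or more of the following reasons". Its reasons include becoming suicidal, homicidal or psychotic, and a worsening condition that needs other treatment. It also states that someone who chooses to stop drug but stays for data collection does not count as withdrawn.

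Follow-up off drug is encouraged in 5.4.1 and 5.4.2. Section 7.3.4 adds that "the participant may discontinue medication at any point and remain in the study for assessments through Week 12".

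Two sections cover early exit, and they differ. Section 5.4.2 says: "If an early exit occurs, the reason(s) for early termination is documented and all Week 12 procedures are conducted". Section 7.3.6 says: "If a participant exits prior to Week 8, all procedures for Week 8 are completed". Section 5.4.2 limits later contact in two situations. One is withdrawal of consent: "No additional study data is collected from the participant after consent has been withdrawn". The other is leaving the interventional part and declining continued follow-up, after which there is no chart access and no further contact.

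The efficacy analysis is by intention to treat (Protocol 10.3, SAP 5.1). It assumes data missing at random and imputes nothing (Protocol 10.4.1, SAP 7.3). The primary response is modelled at Weeks 4, 8 and 12, with Week 8 primary (SAP 9.3).

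**The concern.** Because 5.4.1 separates stopping drug from leaving the study, the wording of 7.5 cannot be read as a drug stop alone. Taken literally, it ends scheduled follow-up for participants whose psychiatric state has deteriorated. CAPS-5 is half of the primary composite, so the reason for exit is plausibly related to the outcome.

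For the same event, a site acting under 5.4.1 could stop the drug and keep the participant in assessments. What is at stake is a small, avoidable amount of outcome-related missing data at the primary time point. Nothing in the analysis corrects for such missingness beyond the missing-at-random assumption and the participant's other visits.

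**Working it through.** **1. The rules side by side, for an exit before Week 8**

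| Question | 7.5 | 5.4.1, 5.4.2, 7.3.4 |
|---|---|---|
| Study drug | stops with withdrawal | may be stopped alone |
| Scheduled Week 8 visit | not kept | may be kept |
| Exit assessment | under 7.3.6 (Week 8 procedures) or 5.4.2 (Week 12 procedures) | the same, if the participant exits |

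Both the Week 8 and Week 12 visits include CAPS-5 and TLFB, so both components are planned at exit under either section. Visits have a window of 7 days either side (7.3.4), so an exit close to Week 8 can fall inside it. For an earlier exit, neither document says whether the assessment counts as Week 8. SAP 9.2 excludes a look-back shorter than 28 days only if "the number of total days included in look-back period is less than one standard deviation of the entire population". A short TLFB record is therefore not automatically dropped, but this rule does not settle which visit the record belongs to.

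**2. The plan's own figure**

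Protocol 10.5 assumes 45 per arm, response of 5/45 on placebo and 17/45 on active, and two-sided alpha of 0.05. Using the arcsine approximation with a correction of 1/(2n) on each proportion:

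- d = 2·asin√(17/45 − 1/90) − 2·asin√(5/45 + 1/90)
- power = Φ(d/√(2/45) − 1.96) = 0.7946

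The table gives 0.795, so the inputs are read correctly. If 4 per arm were lost for reasons unrelated to outcome, the same formula at 41 per arm gives 0.749.

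**3. Effect of outcome-related loss**

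No document gives a rate for the 7.5 trigger. I assume 0 to 4 lost per arm, all Week 8 non-responders, with no use made of their exit or Week 4 data. The observed rate is then k/(45 − lost), where k is the number of responders.

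| Lost, placebo v active | No effect (5 and 5 responders): difference, points | Planned effect (5 and 17): difference, points |
|---|---|---|
| 0 v 0 | 0 | 26.7 |
| 2 v 2 | 0 | 27.9 |
| 1 v 3 | 5/42 − 5/44 = +0.5 | 17/42 − 5/44 = 29.1 |
| 0 v 4 | 5/41 − 5/45 = +1.1 | 17/41 − 5/45 = 30.4 |
| 3 v 1 | 5/44 − 5/42 = −0.5 | 17/44 − 5/42 = 26.7 |
| 4 v 0 | 5/45 − 5/41 = −1.1 | 17/45 − 5/41 = 25.6 |

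The standard error with no effect is √(2 × (5/45) × (40/45)/45) = 0.0663, or 6.6 points. A shift of 0.54 points is 0.08 standard errors and moves the two-sided error from 5.0% to about 5.1%. A shift of 1.08 points is 0.16 standard errors and moves it to about 5.3% (normal approximation).

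**The case against.** The strongest reply is that this is ordinary drafting. Section 5.4.1 gives a general discretion, and 7.5 is a narrower safety rule for acutely unwell people. A reader might infer that the two sections contradict each other. They do not: withdrawal is one of the options in 5.4.1, so a site that follows 7.5 complies with both. Section 7.3.4 also describes the participant's own choice, not a safety decision by the investigator. What stands is the difference between a mandatory and a discretionary rule, and its cost in follow-up.

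The second reply is that safeguards already exist. The medical monitor and lead PIs can authorize a prohibited drug (7.5), and 7.7 allows limited diphenhydramine or hydroxyzine for severe insomnia or agitation, so the rule should apply less often. An exit assessment is planned, and Week 4 responses stay in the model for those who reach Week 4. These replies are largely right and hold the point at minor. They do not secure the outcome at the scheduled time.

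A reader might also infer that the conditional sensitivity analysis in SAP 7.3 would never be triggered. Taken alone, 1 v 3 exits give p = 0.616 and 0 v 4 give p = 0.117 (Fisher's exact test assumed, since no test is named). But SAP 7.3 compares all dropout and missing-data patterns, with attrition of about 30% expected, so these exits alone do not show whether it would be triggered.

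**Conclusion.** The point holds as a minor one. Followed literally, 7.5 gives up scheduled outcomes in participants who are deteriorating, although the protocol elsewhere encourages keeping them in follow-up. Under the stated assumptions the difference shifts by at most about 1.1 points with no effect. Under the planned effect it lies between 25.6 and 30.4 points, against 26.7 with no loss.

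These sizes rest on an assumed count and on every lost participant being a non-responder; the shift would differ if some would have responded. The count is probably small because entry excludes psychotic disorders and a current suicidal plan (5.2). The direction of any bias depends on which arm loses more and is unknown.

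A reader might infer that the primary outcome is lost altogether for these participants, or that the trial's conclusion is at risk. The documents support neither reading: CAPS-5 and TLFB are planned at exit, and the calculated effect is small.

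**What to change.** - **Protocol 7.5:** replace withdrawal from the study with wording such as: *study drug is discontinued and the participant is referred for treatment; unless the participant withdraws consent or declines continued follow-up (5.4.2), the scheduled Week 8 and Week 12 CAPS-5 and TLFB are requested when clinically able.*
- **Protocol 5.4.2:** align with 7.3.6, so that an exit before Week 8 has Week 8 procedures.
- **Optional, SAP 9.3:** add one sensitivity run of the primary model that scores participants who left before Week 8 without a Week 8 assessment as non-responders. The primary analysis stays without imputation.

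The cost is a protocol amendment that needs IRB approval before use (Protocol 13.2) and, if the option is taken, one SAP sentence and one model run. No new procedures are needed, because the visits are already scheduled. The downside is that some Week 8 values will be obtained on non-study psychotropics, which 7.5 restricts partly because they confound. The stated intention-to-treat approach accepts this.
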